Study design	
This study is a multicenter, cross-sectional non-interventional study that aims to set up a registry of patients with IRD in France.
 
This study relies on primary data collection and a cross sectional design. Data will be collected for both patients with prevalent IRD (patients who were already clinically diagnosed with IRD before the inclusion in the study) and patients with incident IRD (patients who were clinically diagnosed with IRD upon their inclusion in the study). To address the primary objective, all patients seen by the physician over the inclusion period following site initiation will be included into the study, on a consecutive and exhaustive basis until a maximum of 1000 patients is reached (registry starter).
 
Given the capacity of sites to screen patients over one year (around 3000 patients), the inclusion of patients into the study will be limited to the first 1000 patients in order to favor the data collection quality by limiting the sites workload. This will also encourage the inclusion of the patients exhaustively, especially for high volume sites for which this registry represents a deep work. However, it should be reminded that this study is a starter study that is planned to be extended to a larger national registry.
 
Since this study is non-interventional, nor clinical interventions neither genetic tests, imaging and assessment schedule will be

	
required as part of this study, and all data will be collected as per physicians' routine practice.
 
Patients included in this study must have either available genetic results upon their inclusion in the study (whether the result of this test is positive or negative) or a genetic testing prescription for IRD (genetic testing through PFMG platform or from a traditional reference public laboratory). Given the delay for obtaining genetic results, the data may be available within approximately 12 months after the test prescription.

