Inclusion and non-inclusion criteria	
Only the patients who meet all the following inclusion criteria can be included in this study:
 
 • All patients, whatever age or gender, clinically diagnosed with IRD or with high suspicion for IRDs based on clinical examination and functional tests (such as fundus exam and ERG), regardless of genetic testing • Patients who attended a consultation at one of the participating centers from SENSGENE network over the inclusion period starting from sites initiation • Patients who had been prescribed a genetic test for IRD prior to or at the date of inclusion. • 
Patients who present at least one of the following non-inclusion criteria cannot be included in this study:
 
 • Patients/Parents/Legally authorized representatives (LAR) opposed to the collection and processing of their medical data/the medical data of their children/the medical data of the person for whom they are LAR; • Patients who are suffering from any other retinal disorder or optic neuropathy that may clinically or genetically overlap with IRD or non-genetic (phenocopy); • Patients/parents/Legally authorized representatives (LAR) refusing genetic testing; • Patients lacking decision-making capacity: Mental incapacity, unwillingness, or language barriers precluding adequate understanding or cooperation.
Conduct of the study	
French reference and competence centers for rare eye diseases are gathered within the SENSGENE network. The Filière de santé maladies rares (FSMR) SENSGENE fulfills national missions around rare sensory diseases with the aim of improving the care of patients, coordinating and encouraging research and developing training and information. Seven French reference and competence centers from the SENSGENE network will be contacted to participate in the study.
 
 • Five coordinating or constitutive reference centers for rare eye diseases: HU-Necker-Enfants Malades-APHP (Paris), CHNO XV-XX (Paris), CHI Créteil, HU Strasbourg, CHU Montpellier. • Two competence centers for rare eye diseases: CHU Nantes and CHU Lille
Required sample size	
This study will set up a registry that will include all eligible patients with IRD who attended a consultation at one of the participating centers from SENSGENE network.

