	
For the Cross-sectional registry no sample size calculation is required as this registry will record patient fulfilling the sets of criteria defined and will allow to have an estimation of the target population at the national level.
 
Given the capacity of sites to screen patients over one year (around 3000 patients), the inclusion of patients into the study will be limited to the first 1000 patients in order to favor the data collection quality by limiting the sites workload. This will encourage the inclusion of the patients exhaustively, especially for high volume sites for which this registry represents a deep work. However, it should be reminded that this study is a starter study that is planned to be extended to a larger national registry.
 
The precision can be estimated for a sample size of 1000 patients while considering 5% loss (patients not evaluable for the primary objective or not meeting all selection criteria).
 
The following table presents the precision and the corresponding 2-sided 95% confidence interval (CI) to describe the distribution of IRD type (proportions varying from 10% to 50% for each modality) and a sample size of 1000 patients.
 
Table. Precision and corresponding 2-sided 95% CI given the proportion of a modality varying from 10% to 50% and a sample size of 1000 patients (5% of non-evaluable patients)
 
  
 	Proportion	
 
 10%	20%	30%	40%	50%	
   
 n	Precision	Precision	Precision	Precision	Precision	
 
 Précision (%)	1.9	2.5	2.9	3.1	3.2	
 
 95% CI	8.1; 11.9	17.5; 22.5	27.1; 32.9	36.9; 43.1	46.8; 53.2	
  
 
The precision (e) is calculated based on the normal approximation using the following formula:
 $e = \sqrt{\frac{1,96^2 * (p - p^2)}{n}}$ 
where p is the proportion of a given modality and n is the number of patients.
		Proportion					10%	20%	30%	40%	50%	n	Precision	Precision	Precision	Precision	Precision	Précision (%)	1.9	2.5	2.9	3.1	3.2	95% CI	8.1; 11.9	17.5; 22.5	27.1; 32.9	36.9; 43.1	46.8; 53.2
	Proportion																													
	10%	20%	30%	40%	50%																									
n	Precision	Precision	Precision	Precision	Precision																									

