Précision (%)	1.9	2.5	2.9	3.1	3.2																									
95% CI	8.1; 11.9	17.5; 22.5	27.1; 32.9	36.9; 43.1	46.8; 53.2																									

Statistical method
	
A descriptive analysis will be conducted on all study endpoints for which data has been collected both for the overall study population and per subgroups of interest where relevant (e.g. patients' clinical characteristics, classification (class 4 and 5), nature of the mutation, the values of visual acuity (VA) and visual field (VF), date of genetic testing, clinical phenotype, type of genetic analysis performed and unsolved patients) as long as that the sizes of the sub-groups are relevant for statistical estimations. The subgroups' modalities and associated endpoints will be detailed in the Statistical Analysis Plan.
 
The following statistics will be provided for quantitative variables: number and proportion of patients with non-missing and missing
																													

	
values per variable, mean, standard deviation (StD), median, first quartile (Q1), third quartile (Q3), minimum and maximum value, the mode (especially for discrete quantitative variables with limited variability).
 
For qualitative variables, the number and proportion of each variable modality will be provided together with the number of missing values. Proportion will be computed based on the population with non-missing data.
 
Exploratory comparison between study subgroups might be considered. Statistical tests will be based on the type and distribution of the variables. All comparison tests will be two-tailed with a standard type 1 error threshold of 5% (significance level).
 
The enrollment of patients in the study will be limited to a maximum of 1000 patients, registered over a variable period of time limited to 12 months.
 
This study design therefore presents bias related to the heterogeneous duration of patients' inclusion which depends on the activity size of each participating physician.
 
In order to take into account the biases associated with this study design and be able to extrapolate results at the national level, an adjustment is planned for descriptive analyses over the registry using a weight applied at center level.

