Expected benefits	
Implementation of an IRD national registry including all data related to IRD and presenting their clinical features may help to deepen the epidemiologic and genetics knowledge of IRDs. No direct benefit to the participating patient is expected from this study but the knowledge generated from this study may benefit future patients.

Provisional schedule	
 -Maximum duration of the inclusion phase: 12 months or the maximum of 1000 patients is reached, whatever occurs first (a) -Maximum duration of participation of each patient: 12 months (b) -Maximum total duration of the study: 24 months (= a+b) -Exclusion from other interventional studies while patients participate to the present clinical trial: None -End of trial: The study end corresponds to the end of the collection of gene testing results of the participation of the last subject in the study.

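### The centre-level weight cannot correct unequal inclusion by visit frequency within a centre, so it does not by itself support national extrapolation

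*Combined protocol and SAP*

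**What the plan says.** All references are to the study synopsis in the combined protocol and SAP.

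- **Entry.** The inclusion criteria admit "Patients who attended a consultation at one of the participating centers from SENSGENE network over the inclusion period starting from sites initiation". Under Study design, patients are taken "on a consecutive and exhaustive basis until a maximum of 1000 patients is reached (registry starter").
- **Stopping.** The Provisional schedule ends inclusion at "12 months or the maximum of 1000 patients is reached, whatever occurs first". The Statistical method section describes patients as "registered over a variable period of time limited to 12 months".
- **Capacity.** Study design and Required sample size both give capacity as the reason for the cap: "Given the capacity of sites to screen patients over one year (around 3000 patients), the inclusion of patients into the study will be limited".
- **Recognised bias and remedy.** Statistical method names one bias: inclusion durations that vary with the activity of each physician. To deal with it and to extrapolate nationally, "an adjustment is planned for descriptive analyses over the registry using a weight applied at center level". The text provided gives no formula for the weight and does not mention how often a patient attends.
- **Claim.** Required sample size says that the registry "will allow to have an estimation of the target population at the national level".
- **Objectives.** The primary and secondary objectives are worded for patients who attended during the inclusion period.

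**The concern.** When entry is by visit and the window is shorter than the usual interval between visits, the chance of inclusion rises with visit frequency. The sample then represents consultations more closely than it represents the patients under care. The plan accepts that unequal inclusion has to be weighted for, but addresses only the part that lies between centres.

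The primary endpoint is the proportion of patients by ORPHA type. If some types are followed more closely than others, their shares are inflated, and a weight that is constant within a centre leaves them so. The planned confidence intervals show sampling error only, so a reader of the extrapolated distribution would have no sign of the problem.

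**Working it through.** **1. The plan's own precision figure.** The formula is e = √(1.96² × (p − p²)/n), with n = 1000 × 0.95 = 950. For p = 20%, e = 1.96 × √(0.16/950) = 2.54 points. All five entries reproduce: 1.91, 2.54, 2.91, 3.12 and 3.18, against 1.9, 2.5, 2.9, 3.1 and 3.2 stated. The 2.5 points at 20% serve as the yardstick below.

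**2. Length of the window.** Inputs from the synopsis: about 3000 screened a year, cap of 1000. Assumed: the share f of screened patients who enrol, even accrual, and sites opening together. Months to the cap = 12 × 1000/(3000 × f).

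| f | 100% | 80% | 70% | 60% | 50% | one third |
|---|---|---|---|---|---|---|
| Months | 4.0 | 5.0 | 5.7 | 6.7 | 8.0 | 12.0 |

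The cap shortens recruitment whenever more than one third of screened patients enrol.

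**3. Chance of inclusion.** For a patient with v visits a year and a window of T months, the chance is min(1, vT/12) if visits are evenly spaced and 1 − exp(−vT/12) if they fall at random. With T = 4:

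| Visits a year | 3 | 2 | 1 | 0.5 |
|---|---|---|---|---|
| Evenly spaced | 1.00 | 0.67 | 0.33 | 0.17 |
| Random | 0.63 | 0.49 | 0.28 | 0.15 |

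With T = 12 these become 1.00, 1.00, 1.00 and 0.50 (evenly spaced), or 0.95, 0.86, 0.63 and 0.39 (random). A full year reduces the imbalance without fully removing it.

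**4. Effect on a reported share.** Assume that a type has a true share of 20% and that all other patients attend once a year. If R is the ratio of inclusion chances, the expected share is 0.2R/(0.2R + 0.8). For T = 4:

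| Visits, type against others | R, even | Share, even | R, random | Share, random |
|---|---|---|---|---|
| 1 to 1 | 1.00 | 20.0% | 1.00 | 20.0% |
| 1.16 to 1 | 1.16 | 22.5% | – | – |
| 1.20 to 1 | – | – | 1.16 | 22.5% |
| 2 to 1 | 2.00 | 33.3% | 1.72 | 30.0% |
| 3 to 1 | 3.00 | 42.9% | 2.23 | 35.8% |

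For 3 to 1 in an 8-month window the share is 27% (even) to 31% (random). In a 12-month window it is 20% (even) to 27% (random).

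**5. What the centre weight does.** If every patient of centre c carries the weight w_c, the weighted share of a type within that centre is w_c × n_type/(w_c × n_all) = n_type/n_all. The weight cancels. It changes only how the centres are mixed.

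An illustration on assumed inputs uses seven centres with 700, 700, 500, 400, 300, 250 and 150 patients a year and type shares of 40%, 35%, 30%, 25%, 30%, 20% and 20%. The true overall share is 945/3000 = 31.5%. The type is seen every 6 months and the others every 12, at even spacing, over 4 months. The type contributes 945 × 4/6 = 630 patients and the others 2055 × 4/12 = 685. The unweighted share is 630/1315 = 47.9%. Weighting each centre by its yearly patients divided by its sampled patients gives 47.5%. The total of 1315 exceeds the cap; stopping at 1000, after about 3.0 months (4 × 1000/1315), leaves both shares unchanged.

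**The case against.** **The objectives are confined to attenders.** This stands. For patients who consulted during the window, taking everyone in order creates no visit-frequency bias. The difficulty begins only with the national wording in Required sample size and Statistical method, which is current text and which the weight is meant to support.

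**No bias in the primary endpoint has been shown.** This also stands. It requires visit frequency to differ by ORPHA type within a centre, and the documents contain no visit data. A reader might infer that children, recently diagnosed patients or those with macular oedema are over-represented. The documents do not support that, and none of these groups is an ORPHA type. At a ratio of 1.1 the 20% share becomes 21.6%, inside the stated precision.

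**Four months is not in the plan.** Correct. It is derived from a screening capacity, while consent, the exclusions and the genetic-test requirement all reduce enrolment. A reader might take four months as planned, or the cap as the sole cause. Neither is supported: the window could be 8 months or longer, durations are expected to vary, and a 12-month window would still under-include patients seen less than yearly. If the 3000 are distinct patients, some of whom return early, the cap could instead be reached sooner than 4 months. The mechanism does not depend on the exact length.

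**This is a starter study.** True, and it limits the consequences. It does not make the extrapolation valid.

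**Conclusion.** The point holds as a limit on the national claim, not on the description of attenders. It is certain that a weight constant within a centre cannot correct unequal inclusion within that centre, and that inclusion favours frequent attenders wherever visit frequency varies and the window is short relative to visit intervals. The cap strengthens this effect.

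Bias in the ORPHA distribution is conditional on visit frequency differing by type, and its size is unknown. The assumed range for a 20% type runs from no bias to 36% to 43% at 3 visits against 1. A difference of only about 1.16 to 1.20 visits against 1 shifts the estimate by the full stated half-width. The plan neither states nor checks that frequencies are equal, so the weight alone does not deliver the extrapolation claimed for it.

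**What to change.** **Main change.** In Required sample size and Statistical method, present the primary ORPHA distribution as describing patients who consulted at the participating centres during the window. Say that the centre weight corrects for different inclusion durations between centres, and do not claim that it alone permits national extrapolation. This needs no new data.

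**If extrapolation is kept**, specify the following in the SAP:

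- From the appointment file, record the number of IRD consultations at the centre in the 12 months before inclusion, excluding the inclusion visit, and whether the patient is newly referred.
- Show the distribution with and without a patient-level visit-frequency weight, as a sensitivity analysis.
- Normalise that weight within centre, so that inclusion duration is not corrected twice.
- Set a separate rule for newly referred patients, and state how other patients with a count of zero are handled.
- State that patients seen less than once a year are only partly corrected.

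The simple weight 1/min(1, visits × window/12), with the inclusion visit counted, should not be used. In a simulation of the 3-to-1 random-visit case (20% true, about 36% unweighted), it leaves about 25% when no patient is new. It gives 36% to 37% when half of the frequent type are newly referred, and 45% when all of them are.

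**Cost.** The main change narrows the headline claim. The optional part adds one retrospective count with a newly-referred flag, a few lines in the SAP, and a somewhat larger variance in the sensitivity analysis.

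### If the stated 12- and 24-month limits govern, late genetic results drop out of the time-to-molecular-diagnosis summaries, and the interval is biased short in patients diagnosed and tested at inclusion

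*Combined protocol and SAP*

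**What the plan says.** All references are to rows of the synopsis in the combined protocol and SAP.

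- **Entry.** Study design requires either results already available ("whether the result of this test is positive or negative) or a genetic testing prescription for IRD"). Inclusion and non-inclusion criteria allow the prescription to date from the day of inclusion.
- **Turnaround.** Study design expects that "the data may be available within approximately 12 months after the test prescription". No distribution is given.
- **Patient mix.** The cohort combines prevalent cases ("patients who were already clinically diagnosed with IRD before the inclusion in the study") and incident cases ("patients who were clinically diagnosed with IRD upon their inclusion in the study"). Neither share is stated.
- **Follow-up.** Provisional schedule limits each patient to 12 months and the whole study to 24 months. The same row also ties the end of the study to completion of genetic-result collection for the last patient. It does not say which statement prevails.
- **Endpoints.** Secondary endpoints include the time from clinical diagnosis to definitive molecular diagnosis, the time from a previous molecular test to that diagnosis, and the proportion of unsolved patients.
- **Analysis.** Statistical method: "The following statistics will be provided for quantitative variables: number and proportion of patients with non-missing and missing" values, followed by mean, standard deviation, median, quartiles and range. For categorical variables, "Proportion will be computed based on the population with non-missing data". Summaries are planned "both for the overall study population and per subgroups of interest where relevant". Subgroup "modalities and associated endpoints will be detailed in the Statistical Analysis Plan". Pending results and censoring are not mentioned.

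**The concern.** The expected turnaround is about as long as the longest permitted follow-up, so a patient whose test is prescribed on the day of inclusion has no margin for a late result. A patient still waiting at the limit has an interval known to exceed the time already elapsed. A summary of observed values discards that information and treats the patient as missing. The patients lost this way are, by construction, those with the longest turnaround, so the loss is not random with respect to the quantity being estimated.

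At stake are the two intervals ending at the molecular diagnosis and, less directly, the unsolved proportion and the gene and variant distributions. These are secondary and descriptive, but genetic diagnosis is the first secondary objective listed and the study is meant to seed a national registry, so the convention may be carried forward.

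**Working it through.** **Inputs from the documents.** Turnaround of about 12 months; participation limit of 12 months; study limit of 24 months; same-day prescription allowed; observed-value summaries; stated precision of 3.2 points at a proportion of 50%.

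**The plan's own figure.** With 5% loss, n = 950 and e = 1.96 × √(0.25/950) = 3.18, which rounds to the stated 3.2 points. It reproduces, is not in dispute, and serves below only as a yardstick.

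**Direction in patients diagnosed and tested at inclusion.** Clinical diagnosis, prescription and inclusion coincide. With a 12-month limit every recorded interval is at most 12 months. If any true interval is longer, the mean and median of the recorded values lie below the true ones. This step needs no distributional assumption. Late negative results contribute no duration either way.

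**Size in that subgroup (assumed).** Take 12 months as the 90th percentile of a log-normal turnaround, so that 10% are pending. Then μ = ln 12 − 1.2816σ, the true mean is exp(μ + σ²/2), and the recorded mean is the true mean × Φ(1.2816 − σ)/0.9.

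| σ | True mean | Recorded mean | Shortfall (months) |
|---|---|---|---|
| 0.3 | 8.55 | 7.95 | 0.60 |
| 0.5 | 7.16 | 6.23 | 0.93 |
| 0.8 | 5.93 | 4.51 | 1.42 |

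At σ = 0.5 the median falls from 6.32 to 5.94 months. If 12 months were instead the median turnaround, half would be pending. The recorded median would be the lower quartile, 12 × exp(−0.6745σ), which is 10.5, 9.2 or 8.0 months for σ = 0.2, 0.4 or 0.6, against a true 12.

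**Direction in the pooled cohort.** Recorded mean − true mean = p × (mean of recorded − mean of pending), where p is the pending share among patients who will eventually have a definitive diagnosis. The sign therefore depends on whether the dropped intervals lie below or above the recorded mean. Assume 50% tested at inclusion and 10% of those pending, so p = 0.05, with σ = 0.5. Pending turnaround then averages (7.16 − 0.9 × 6.23)/0.1, about 15.56 months from unrounded values. M is the mean interval in patients with results at entry.

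| Scenario | True | Recorded | Difference (months) |
|---|---|---|---|
| Tested at inclusion are all incident, M = 12 | 9.58 | 9.27 | −0.31 |
| Same, M = 24 | 15.58 | 15.58 | 0.00 |
| Same, M = 60 | 33.58 | 34.53 | +0.95 |
| Tested at inclusion were diagnosed 60 months earlier, M = 24 | 45.58 | 44.00 | −1.58 |

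For example, with M = 12 the recorded mean is (0.5 × 12 + 0.45 × 6.23)/0.95 = 9.27.

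**Unsolved proportion.** Let f be the share tested at inclusion and q the share of those pending. Dropping pending patients produces an error of f × q × (difference in unsolved rate between returned and pending tests). With f = 30, 50 or 70%, q = 10% and an assumed difference of 20 points, this is 0.6, 1.0 or 1.4 points, of either sign, and zero if there is no difference. With q from 5% to 20% the range is 0.3 × 0.05 × 20 = 0.3 to 0.7 × 0.20 × 20 = 2.8 points. All are below the 3.2-point yardstick, but the error grows in proportion if more results are late.

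**The case against.** The strongest reply is that the study may simply wait. The end-of-study sentence can be read as continuing collection until results are in, and the 12-month participation period looks chosen to match the expected turnaround. On that reading the truncation largely disappears. This stands as a condition on the whole point, but it does not remove it: the same row states the two maxima and gives no order of precedence. The two limits also differ in effect. If only the 24-month total bound collection, early enrolees could have intervals beyond 12 months recorded, and the loss would fall mainly on late enrolees.

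Second, the signed bias concerns a group that the plan does not say it will report separately. The subgroup list is given as examples and names neither patients tested at inclusion nor prevalent versus incident status. That is fair, and it is why no direction is claimed for the overall summary.

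Third, missing counts will be reported and date of genetic testing is a named subgroup, so the loss would be partly visible. That is also fair. A count does not correct a truncated mean or median, however, and does not separate results still awaited from data never collected.

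Fourth, only synopsis-level text is available and detail is deferred to the SAP. A definition of unsolved or a rule for pending results may exist there, and their absence here is mostly missing detail. The observed-value summary of durations is different, because it is stated.

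Finally, the sentence on non-missing denominators governs proportions only. The argument about durations rests on the separate sentence on quantitative variables.

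**Conclusion.** The point holds conditionally. If the 12- and 24-month maxima govern, the stated summaries truncate the intervals that end at the definitive molecular diagnosis. Among patients clinically diagnosed and tested at inclusion the result is biased short whenever any true interval exceeds 12 months. The size cannot be derived from the documents; 0.6 to 1.4 months on the mean rests on an assumed 10% pending and a log-normal turnaround.

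Three stronger readings are tempting, and the documents support none of them:

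- A reader might infer that the overall time to molecular diagnosis is understated. The mix of prevalent and incident patients is not given, and plausible mixes move the pooled mean down, up or not at all.
- A reader might infer that the unsolved proportion is materially biased. The non-missing denominator most naturally excludes pending patients. Any error then depends on whether turnaround is related to outcome; it is of unknown sign and probably small.
- A reader might infer that the main result is at risk. The primary endpoint, type of IRD, does not directly depend on a returned genetic result.

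Severity is minor to should-fix, since the endpoints are secondary and descriptive and the remedy is cheap.

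**What to change.** 1. **Cut-off.** Reconcile the end-of-study sentence in Provisional schedule with the 12- and 24-month maxima, and state one cut-off for genetic results in the SAP.
2. **Durations.** For patients without a result at inclusion, replace observed-only summaries with the cumulative incidence of definitive molecular diagnosis, treating a completed negative test as a competing outcome and censoring pending patients at the cut-off. Use each endpoint's own origin: clinical diagnosis for the first interval, the previous test for the diagnostic-odyssey interval. Apply delayed entry at inclusion for every patient whose origin precedes inclusion. Use the planned centre-level weight, give a median only if it is reached, and report these patients separately from those with results at entry.
3. **Status.** Report solved, unsolved (test complete, no molecular diagnosis) and pending over all included patients, with the same weights. Label the unsolved proportion among completed tests as such, and add bounds that count pending patients as none or all unsolved.

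The cost is one dated status field, SAP wording, a clarification of the schedule and a little more analysis. No extra visits or tests are needed.
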